#### 10 INVESTIGATORS OBLIGATIONS

#### 10.1 Data recording

The Principal Investigator is ultimately responsible for the quality of data recorded in the Case Report Form. These should be a complete and accurate record of the patients' data collected during the study.

#### 10.2 Storage of study documentation

The documentation for this study should be stored securely, both in written and electronic formats. All data stored electronically should comply with the Data Protection Act. The investigator should arrange for retention of Case Report Forms, source records, and other supporting documentation for a minimum of 15 years.

#### 10.3 Notification of primary care physician

It is the investigator's responsibility to notify primary care physicians of their patient's participation in the study, including its nature and duration, and expected benefits or possible adverse events. We will ask the primary care physician to notify the clinical investigators if a trial participant dies following discharge up to day 28 following admission. This will reduce the likelihood of the trialists contacting the patient or his/her carer for information post-mortem.

#### 10.4 Reporting

The Principal Investigator MUST be notified as soon as possible (usually within 24 hours) by the study nurse of all deaths that occur within 28 days of admission and of the patient's study group. It is conceivable that early identification of *S. pneumoniae* infection by rapid near patient tests could result in streamlining of antibiotics from broad-spectrum to narrow spectrum antibiotics by the medical team caring for the patient, which could be detrimental if the patient had polymicrobial infection (i.e., infection with several pathogens).

The Principal Investigator, following discussion with members of the Trial Steering Committee, would inform the Chairman of the Independent Data Monitoring Committee (IDMC) of any concerns that patient welfare was being adversely affected by the study. The Principal Investigator would seek evidence of the following with each death: (i) Occurrence of polymicrobial infection; (ii) influence of rapid near patient tests on antibiotic prescribing for the deceased; and (iii) poor antimicrobial activity of the newly prescribed antibiotic against the causative pathogen(s), other than *S. pneumoniae*.

The Principal Investigator would immediately report to the Chairman of the Independent Data Monitoring Committee (IDMC) any evidence that patients whose *S. pneumoniae* infection was diagnosed by rapid tests had a worse outcome than those diagnosed by conventional tests, which could not have arisen by chance alone.

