It is possible that patients with a positive rapid pneumococcal antigen test result may receive a single antimicrobial agent, and that mortality of patients with polymicrobial infection including S. pneumoniae is increased. Oosterheert *et al* recently undertook a systematic review to assess whether treatment with a  $\beta$ lactam plus macrolide or quinolone monotherapy is truly superior to beta-lactam treatment alone. Eight relevant studies were selected. In six, significant reductions in mortality were found; in one, a reduction in hospital length of stay was found; and in another no beneficial effects could be demonstrated for treatment regimens with fluoroquinolone monotherapy or combinations of  $\beta$  -lactams and macrolides. The studies supporting the recommended treatment regimen were designed as non-experimental cohort studies. As a consequence, confounding may have influenced the results. In addition, the outcomes showed several inconsistencies. The authors concluded that a randomised controlled trial is warranted to circumvent the methodological flaws in the designs of the currently available studies, particularly as the addition of macrolides or treatment with fluoroquinolones may lead to enhanced antibiotic resistance, increased side effects, and healthcare-related costs. In Leicester, the recommended empiric therapy for patients hospitalised with CAP consists of monotherapy with a β-lactam agent or erythromycin if allergic to penicillin. Addition of a macrolide is not recommended unless the pneumonia is severe and therapy is adjusted 'as appropriate' at 48 hours if there has been no improvement. Although the available evidence does not indicate that rapid near patient pneumococcal antigen testing will adversely affect patient outcome, we plan that an independent Data Monitoring Committee conduct interim analyses to ensure that patient welfare is not adversely affected.

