#### 1.8 Diagnostic tests pneumococcal pneumonia

Diagnosis of pneumococcal pneumonia is complicated by the lack of a diagnostic reference standard that is highly sensitive and specific. Despite being the single most important pathogen causing CAP, *S pneumoniae* is undoubtedly underdiagnosed due to limitations of conventional tests. Limitations of Gram stain and culture of sputum include failure to obtain a sputum sample – only a minority of patients are able to produce sputum samples; the overall diagnostic yield of sputum examination is very low (<25%); and isolation of *S pneumoniae* from sputum may represent colonisation. Historically, blood cultures were considered a standard of care for the investigation of patients with CAP. Positive blood culture results are found in <10%

of patients with CAP. The test is rarely useful, as positivity becomes evident no earlier than 24h after obtaining the specimen, and results typically have little influence on therapeutic decisions and outcomes. However, a review of patients with confirmed pneumococcal pneumonia, found that 42% of patients with positive blood culture results had their treatment changed as a result. Since the overall prevalence of  $\beta$ -lactam resistance remains low in the UK, rapid near patient testing for pneumococcal infection could influence therapeutic decisions.

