#### 4. URINE

A freshly voided urine sample will be collected from all study participants into standard containers for:

- GROUP 1 ONLY: Near patient testing for pneumococcal antigen using the Binax NOW test by the Study Nurse on the MAU/Ward.
- GROUP 2 ONLY: Prompt testing in the laboratory for pneumococcal antigen using the Binax NOW test on fresh 20 ml concentrated urine.
- GROUP 3 ONLY: Deferred testing for pneumococcal antigen using the Binax NOW test on stored 20ml concentrated urine.
- **GROUP 1 ONLY**: Patients randomised to Group 1 will have near patient tests for pneumococcal antigen done by the study nurse in an area of the MAU/ward where urinalysis is done routinely. A description of the test kit and obstructions for doing the test is provided in Appendix X. On completion of the test the Study Nurse will:
  - (a) Record the test result in the CRF;
  - (b) Inform the team (i.e., the responsible nurse and/or doctor) that is providing clinical care of the patient of the rapid near patient test result (i) verbally; and (ii) by insertion of an adhesive label in the notes. The clinical team should be told that a negative test does not exclude infection with with *S. pneumoniae*.
  - (c) Document in the CRF the time that the team was informed, and who was told.

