#### 9 SCHEDULING OF THE STUDY

#### Year 1: 1 June 2005 - 31 May 2006

1. **June** – **August 2005:** Purchase computers, refrigerators, & diagnostic kits and other consumables for first year; appoint three research nurses; post-doctoral RA; and MLSO; set up committees for

trial management and independent review & initiate work programme; generate randomisation code; produce and print CRF and develop trial database.

- 2. July August 2005: Transfer of PCR Technology to Leicester; review SOP's in UHL Virology Laboratory.
- 3. August 2005: Pilot study of CRFs, patient recruitment, specimen handling, etc, and refinements as necessary.
- 1 September 2005 30 June 2006: Year 1 clinical trial; Trial Management Committee to review progress after 4 weeks of operation & continue with ongoing audit of patient recruitment, data entry into CRFs.
- 5. **December 2005 & March 2006:** Independent Data Monitoring Committee to hold their 1st & 2nd meetings and decide future meetings.
- 6. Nov 2005, Jan 2006, Mar 2006, May 2006: Review by Trial steering Committee of progress of Year 1 clinical trial.

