#### Year 2: I June 2006 - 31 May 2007

- June August 2006: Carry out PCR, serology, & analysis of stored urine specimens; Audit and analysis of Year 1 data: purchase diagnostic kits and other consumables for second year. Prepare Year 1 analytical report.
- 2. **1 September 14 December 2006:** Collate and analyse all diagnostic data from Year 1, including serological data; Prepare Year 1 analytical report by 14 December 2006.
- 3. **1 September 2006 30 June 2007:** Year 2 clinical trial; continue with ongoing audit of patient recruitment, data entry into CRFs.
- 4. February 31 May 2007 Carry out 'Ease of test' study during February-May.
- 5. Nov 2006, Jan 2007, Mar 2007, May 2007: Review by Trial steering Committee of progress of Year 1 and 2 data.

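### The only comparative safety trigger in 10.4 compares patients by how they were diagnosed, not by randomised group, and waits for chance to be excluded, so it can delay detection of harm

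*Protocol*

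**What the plan says.** Sections 3.5 and 10.4 of the protocol name one specific harm: early identification of pneumococcus could lead to narrower antibiotics in a patient who also has other pathogens. Section 10.4 then sets out what reaches the IDMC.

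- **Comparative trigger.** The principal investigator reports immediately on signs that pneumococcal cases whose "infection was diagnosed by rapid tests had a worse outcome than those diagnosed by conventional tests, which could not have arisen by chance alone". No outcome, test, significance level or number of looks is attached.
- **General route.** After discussion with steering committee members, the principal investigator tells the IDMC chairman "of any concerns that patient welfare was being adversely affected by the study". No chance condition applies.
- **Review of deaths.** "The Principal Investigator would seek evidence of the following with each death": polymicrobial infection, influence of the near patient test on prescribing, and poor activity of the new antibiotic against the other pathogens.

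Section 1.5 adds: "we plan that an independent Data Monitoring Committee conduct interim analyses to ensure that patient welfare is not adversely affected". Section 9 has the "Independent Data Monitoring Committee to hold their" first two meetings in December 2005 and March 2006 and decide on later ones.

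On testing, section 6.1.14 (Urine) gives Group 1 the antigen test on the ward and Group 2 a prompt laboratory test. Group 3 gets "Deferred testing for pneumococcal antigen using the Binax NOW test on stored 20ml concentrated urine". Section 9 schedules this work for June-August 2006 ("Carry out PCR, serology, & analysis of stored urine specimens") and for May-August 2007.

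**The concern.** The trigger is meant to protect patients while recruitment is under way, and two features work against that.

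First, the sets compared are defined by how a case came to light. Randomisation does not balance them, although section 7.6 puts all process and clinical outcomes on an intention-to-treat footing. In season, a Group 3 patient is a known pneumococcal case only if blood or sputum culture is positive, whereas Groups 1 and 2 also contribute antigen-positive, culture-negative cases. If culture-positive patients have worse outcomes to begin with, the conventional set carries a higher baseline mortality and an excess in the rapid set is hidden.

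Second, making the report depend on excluding chance turns a prompt to look into something close to a significance test on a handful of deaths. A real increase would usually fail it.

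At stake is how soon the IDMC is alerted to the harm the protocol itself anticipates. A delay during recruitment cannot be made good at final analysis.

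**Working it through.** **Inputs from the protocol**

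- Pneumococcal cases (7.1): 747 / 3 = 249; 249 / 3 = 83 in Group 1; remainder 166. The protocol's 83 and 166 are reproduced.
- Mortality from pneumococcal pneumonia in hospitals (1.5): about 2.5%.
- Culture yield (1.8): "Positive blood culture results are found in <10" per cent of patients with community-acquired pneumonia, and below 25% for sputum examination.
- Power (7.4): calculated for diagnostic accuracy, length of stay and isolation; none for mortality.

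**Assumed, because 10.4 gives nothing:** alpha 0.05, Fisher's exact test; true mortality in rapid-diagnosed patients 5% (a doubling) or 10%, against 2.5%.

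**Step 1. Are the two sets like for like?** Blood and sputum cultures go to all groups. The antigen result is available promptly in Groups 1 and 2, but in Group 3 only once stored urine is tested, around or after the end of each season. At the December 2005 and March 2006 meetings, Group 3's known cases are therefore culture-positive only. The sets are also loosely defined. Section 6.2.1 lists Group 2's laboratory antigen test under rapid tests, while 7.1 counts everyone outside the near patient group as tested by traditional methods. A patient in Group 1 or 2 can be positive by both routes.

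**Step 2. How large could the selection effect be?** This is an illustration resting on assumptions. Let a share b of cases be bacteraemic, with mortality m1 in these and m2 in the rest. Culture finds all bacteraemic cases and 25% of the rest; the antigen test finds 85% and 80%. With no treatment effect:

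- culture-diagnosed mortality = (b·m1 + (1−b)·0.25·m2) / (b + (1−b)·0.25)
- antigen-diagnosed mortality = (b·0.85·m1 + (1−b)·0.80·m2) / (b·0.85 + (1−b)·0.80)

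| b | m1, m2 | Culture | Antigen | Ratio |
|---|---|---|---|---|
| 25% | 8%, 1% | 5.0% | 2.8% | 1.77 |
| 15% | 8%, 1% | 3.9% | 2.1% | 1.85 |
| 25% | 4%, 2% | 3.1% | 2.5% | 1.25 |
| 15% | 4%, 2% | 2.8% | 2.3% | 1.22 |
| either | equal | same | same | 1.00 |

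The ratio runs from 1.0 to 1.85. At the upper end, true mortality in rapid-diagnosed patients would have to rise about 1.8-fold before the sets even looked equal.

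**Step 3. What does the chance condition do?** Set selection aside and sum the binomial probabilities of every pair of death counts for which Fisher's p ≤ 0.05.

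| Cases, rapid v conventional | 5% v 2.5%, two-sided | one-sided | 10% v 2.5%, two-sided | one-sided |
|---|---|---|---|---|
| 83 v 83 (whole trial) | 5% | 10% | 39% | 54% |
| 83 v 166 (whole trial) | 16% | 19% | 67% | 70% |
| 28 v 55 (a third of the way) | 6% | 6% | 28% | 28% |
| 27 v 27 (one season alone) | 0.1% | 0.5% | 3% | 7% |

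A normal approximation is kinder but leads to the same conclusion: for a doubling, 13% (83 v 83) and 20% (83 v 166) two-sided, 21% and 29% one-sided.

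In counts, 83 v 166 with 4 conventional deaths (166 × 0.025 = 4.15) needs 7 deaths in 83 (8.4%; p = 0.046), since 6 give p = 0.088. For 27 v 27 with no conventional deaths, 5 give p = 0.051 and 6 give p = 0.023.

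**Step 4. Would comparing randomised arms be enough?** No. The 83 v 83 row already treats the arms as like for like and gives 5% (two-sided) for a doubling. By the normal approximation, 80% power would need 906 pneumococcal cases per arm. The chance condition has to go as well.

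**The case against.** The strongest reply is that this sentence is not the only route to the IDMC. The general route in 10.4 carries no chance condition, and the review of each death looks directly for the feared mechanism without needing a comparator. The reassurance in 1.5 rests on IDMC interim analyses, whose tables may be set out in a charter or analysis plan not shown here. That stands. A reader might infer from the trigger that real harm is masked throughout recruitment, or that the welfare promise in 1.5 is empty. The documents do not support either: these routes can bring harm to light. They are partial, though. The general route is discretionary and passes through the steering committee, the death review compares nothing, and the protocol specifies no interim comparison.

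The wording may also be shorthand for randomised groups. Objective 7 uses similar language, while the endpoints in 7.5.1 are given for Groups 1, 2 and 3, and 7.3 sets one definition of positivity. That is possible, but 10.4 does not say it, and in season the 7.3 definition cannot be applied in full to Group 3.

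Timing limits the point too. On the schedule, by version 6 of November 2007 stored urine from two seasons would have been tested. The culture-only limit therefore applies to the season in progress, not to all monitoring.

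Two figures should not be read as the size of the problem. The 0.1% is a single-season worst case that discards earlier data. The 1.8-fold ratio rests on 8% v 1% mortality, which no document gives. The protocol does not say that culture-positive patients are sicker, and 1.8 notes that sputum isolates may reflect colonisation.

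**Conclusion.** The point holds in a limited form. The one comparative safety trigger the protocol states uses sets that randomisation does not make comparable, and its chance condition makes it a weak alarm. For a doubling of mortality from about 2.5%, it would respond with a probability of about 5-19% over the whole trial (Fisher's exact test, assumed alpha 0.05, 83 v 83 or 83 v 166), and less within a season. The direction of the selection bias, towards understating harm, depends on culture-positive cases being sicker. Its size is not established; the illustration spans 1.0 to 1.85. The power result does not depend on that assumption.

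The conclusion is that this trigger can delay detection of harm while other, softer safeguards remain. It is worth correcting because the protocol itself fixes the rule and the repair uses data already collected.

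**What to change.** Reword the trigger in 10.4 as follows.

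- Each IDMC meeting receives 28-day deaths, intensive care admissions and ventilatory support by randomised group (1, 2 and 3), with differences and confidence intervals.
- These are shown for all enrolled patients and for those with a diagnosis of pneumonia on admission, which does not depend on the allocated test.
- Pneumococcal subgroups are compared only where one case definition has been applied equally to all three groups, which for Group 3 means after its stored urine has been tested.
- The requirement that a difference be beyond chance is deleted as a condition for reporting. The IDMC weighs chance when it sees the data.

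The general route and the review of each death stay as they are.

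The cost is one paragraph and a by-group table. Section 10.4 already has every death within 28 days, with its study group, notified to the principal investigator, usually within 24 hours, and 6.2.7 already records intensive care and ventilatory support. The downside is small: the IDMC will see some chance imbalances.

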#### **10.5 Protocol amendments**

All amendments that have an impact on subject risk or the study objectives, or require revision of the informed consent document, must receive approval from the Ethical Committee prior to their implementation.

#### 11 LIKELY OUTPUTS FROM THE STUDY

A substantial amount of information will be generated by the studies. Publications arising out of the work will focus on:

- *Test parameters:* The diagnostic accuracy (sensitivity, specificity, positive and negative predictive values) and discrepant analysis of molecular and near patient diagnostic tests, in comparison to traditional and other laboratory methods. The ease of use and speed of rapid, near patient; rapid molecular; and traditional laboratory tests for influenza, RSV, and *S. pneumoniae*.
- *Clinical outcomes:* Including the impact of rapid test results on antimicrobial prescribing, the appropriate use of isolation facilities; the length of hospital stay; admissions to Intensive Care; ventilatory support; deaths; and Quality-of-life, as measured by EuroQol, and quality adjusted life years (QALYs) generated during the 28 days after admission.
- *Financial:* The costs of diagnostic tests. Cost-savings associated with earlier use of narrowspectrum antibiotics, oral therapy, or avoidance or discontinuation of antibiotics. Costs associated with inpatient stay and post-discharge, up to a maximum of 28 days after admission. Costeffectiveness of rapid molecular and near patient diagnostic tests.
- Admission rates: for influenza, RSV, and S pneumoniae in the target population.

## PROTOCOL FOR COLLECTION OF HEALTH ECONOMIC DATA

# The EuroQol questionnaire for this study will be completed at baseline, 7 days and 28 days and the same procedure should be followed.

- 1. Before completing the EuroQol questionnaire at each time point the research nurse will complete the Quality of life assessment form.
- 2. There are four ways the EuroQol questionnaire can be completed:
  - a. Subject is unconscious and is declared as such.
  - b. Self-completion by the respondent.
  - c. Interview by the research nurse for those for example who are visually impaired or for some other reason cannot self complete. At the 7 and 28-day time points, if they have been discharged, the research nurse will carry out a telephone interview.
  - d. For those who cannot complete the questionnaire due to other circumstances, for example they are too ill or are cognitively impaired, a proxy should be identified (ideally somebody who is familiar with the subject).

Those subjects who are either unconscious or have a proxy response at an early time point may become well enough to self-complete the EuroQol at either the 7day or 28 day time point. These subjects should then self-complete (or interview complete) the EuroQol.

- 3. If a proxy is being used then the research nurse should fill in the subjects name in the lines provided on pages 2 and 3 and the box on page 3.
- 4. Once the questionnaire as been completed the research nurse should ensure that all sections of the EuroQol have been completed (one answer in each section).
- 5. All completed questionnaires should be stored together with the subjects Quality of life assessment form.

#### 7 and 28 day follow up questionnaires for those who have been discharged.

- 1. There is an additional questionnaire to be completed if the subject as been discharged.
- 2. If a proxy is to be used then the same proxy should be used to complete all questionnaires for the subject if possible.
- 3. The research nurse should obtain the proxy's address and post the questionnaire to them with a stamped addressed envelope before the 7 or 28-day time point.
- 4. At the 7 day time point the respondents should be sent the appropriate EuroQol (either selfcomplete or proxy). Those who require it should have a telephone interview (see point C above)
- 5. At 28 days all discharged subjects should be sent appropriate 28 day questionnaire (either selfcomplete or proxy). Again, those who would be unable to complete a questionnaire should have a telephone interview (see point C above).
- 6. Non-responders should be sent another form and reminder 7 days after this period.

Version 1 18th May 2005

## EuroQol Assessment – Inpatient (Baseline, 7 and 28 days after admission)

REMINDER – ONLY TEXT IN ITALICS SHOULD BE READ OUT TO THE INTERVIEWEE. BOLD CAPITALS ARE INSTRUCTIONS TO THE INTERVIEWER. PLEASE FILL IN ALL RELEVANT SECTIONS. ANSWER YES/NO QUESTIONS BY CIRCLING APPROPRIATE NUMBER.

## FILL IN RESPONDENT DETAILS BEFORE INTERVIEW

Admission	date:	/	, j	/

Study Number: \_\_\_\_\_

## **Baseline EuroQol**

Date of interview: \_\_\_/\_\_/\_\_\_ Interviewer Name: \_\_\_\_\_

Is patient unconscious?

Yes1	DISCONTINUE INTERVIEW
No2	

**IF PATIENT IS ABLE TO RESPOND TO INTERVIEWER SAY:** Hello. Thank you for agreeing to take part in this study. We are interested in how you feel today. To find this out we would like you to fill in a short questionnaire. Do you feel able to complete this questionnaire yourself?

Is patient able to self-complete Euroqol?

Yes1	GIVE PATIENT SELF COMPLETE EUROQOL AND
	ATTACH COMPLETED FORM TO BACK OF THIS
	FORM
No2	COMPLETE SECTION 2

